Ethiopia remains the country with the greatest trachoma burden [2]. It is estimated that 30% of Africa's trachoma burden is in Ethiopia. More than 80% of its population of 90 million live in rural areas and 37% live on less than a dollar a day [21]. Half the population travel significant distances to access safe drinking water and sanitation coverage is lower than expected [22]. A national survey conducted in Ethiopia in 2010 showed that access to water supply and sanitation was 52% and 63% respectively [23]. These environmental and living conditions are believed to create the ideal situation for trachoma to flourish. In Oromia, both active trachoma and trichiasis are significant public health problems. The most recent GTMP data published for this region shows an estimated overall prevalence of TF1-9 of 23.4% across 252 districts [24]. In 46% of surveyed districts, TF1-9 prevalence was >30% in 126 of 252 districts [25].

[figure not shown]

Figure 1: Active Trachoma Prevalence in Ethiopia (Global Trachoma Atlas) [25].

Sample size

During the pilot work for this study, 1/9 (11%) children with ocular discharge before washing still had discharge after washing with water and soap, whereas 11/15 (73%) children still had discharge after washing with water alone, an difference of 62% (Czerniewska et al., 2020). We expect the reductions in facial Ct DNA to be more modest. Assuming 90% of children with facial Ct before washing still have facial Ct after washing in the water only arm and 60% of children with facial Ct before washing still have facial Ct after washing with water and soap, 47 children with Ct on their faces will be needed in each trial arm. This target will be inflated by 10% to account for people being lost to follow-up.

This sample size was calculated using the following formula:

$$n = (Z_{\alpha/2} + Z_6)^2 * (p_1(1-p_1) + p_2(1-p_2)) / (p_1-p_2)^2$$

Where $Z_{\alpha/2}$ is the critical value at our pre-determined confidence level (95%) adjusted using Bonferroni's correction for multiple comparisons to accommodate our three-arm design (0.05/3=0.017, critical value for 0.017=2.573), Z_{β} is the critical value for the study power (80%), and p_1 and p_2 are the proportions of children with detectable Ct on their faces immediately after washing in each group.

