Based on previous data from the Stronger SAFE project, we expect 50% of children with severe inflammation (F3 and/or P3) to have ocular infection and 60% of those children with ocular Ct infection to have Ct on their faces (Last $et\ al.$, 2020). Therefore, to recruit (3 x 47 =) 141 children with facial Ct, we need (141/0.6 =) 235 children with ocular Ct, for which we will need to enrol at least (235/0.5 =)

470 children with F3 and/or P3 to achieve our sample size. If 5% of our screened sample have F3/P3, we will need to screen 9,400 children to achieve this sample.

Participant eligibility and recruitment

Children aged 1-7 years will be the primary target population, as both active trachoma and the presence of ocular infection disproportionately affecting young children (18). In addition, as this age group is particularly affected by trachoma, it is children that need effective interventions to reduce *Ct* on faces.

A total of 470 participants will be selected purposively following a screening process. Following verbal parental consent, children aged 1-7 years will be assembled in a central point in each study *kebele* (community) and screened for clinical signs of TF or trachomatous inflammation—intense (TI) by a Tropical Data certified ophthalmic nurse with experience grading trachoma. Both simplified WHO grading and FPC (follicles, papillary hypertrophy and diffuse infiltration, conjunctival scarring) grading system will be performed. Children with severe TF (F3) or TI (P3) will be invited to take part in the study. A subsample may be tested for conjunctival *Ct* infection using a rapid diagnostic test (RDT), such as DjinniChip (19), as a quality assurance mechanism to determine whether the clinical screening is successfully identifying children with infection. Children who have clinical trachoma not meeting the criteria for enrolment (ie. mild TF, F2) will be treated for trachoma at this point based on clinical positivity.

We will identify high prevalence communities for recruitment through analysis of programmatic survey data and target those communities for recruitment. When a case of infection is identified, a snowball method will be used to recruit contacts, playmates and siblings. To recruit 470 individuals with severe inflammation, we plan to screen approximately 9,400 children aged 1-7 years. These estimates are based on prior experience in region from the Stronger SAFE study (20).

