Analyses will be 'per-protocol' so efficacy can be assessed, but will be restricted to children with *Ct* on their face at baseline as determined by PCR. Participants will be analysed according to the protocol they performed. Primary comparisons will be between Protocols A and B and will compare the proportion of participants without *Ct* detected on faces immediately following face washing according to each protocol. In secondary analysis we will look at *Ct* removal following Protocol C, removal of oculo-nasal discharge following Protocols A-C and mean log₁₀ reduction in load of *Ct* on faces immediately following each Protocol. A further secondary analysis will compare how quickly the load of Ct builds up on the faces of infected children, following removal by each of these four methods. Regression analyses will be performed to evaluate the relative efficacy of the various cleaning methods for removing Ct from faces using 'washing with water' as the comparison. Another secondary analysis will assess the viable load of Ct found on the SuperTowel® samples after use, to give an indication of their potential role as fomites in transmission.

We will also compare the ability of a novel, quantitative metric vs current metrics (i.e. signs of ocular and nasal discharge), to predict recent personal cleaning practices, across the four methods.

We will look for presence of Ct in stool as determined by PCR.

As ocular infection is assessed through both rapid test and PCR, we also have the opportunity to compare the results to evaluate the diagnostic ability of the rapid test.

Data management

Data from the study will be jointly managed by the LSHTM and FHF team in Ethiopia, coordinated by the Ethiopian Project Manager and the PI. Data will be entered at the time of collection via electronic data capture on password protected Android Devices using the Open Data Kit (ODK) secure data capture system provided by LSHTM http://opendatakit.lshtm.ac.uk/. All data is automatically encrypted on the Android devices when the ODK form on the Android devices is filled and finalised. The ODK Collect app uses the public encryption key along with an encryption algorithm to convert the data in to an encoded (encrypted) form. Once the form is finalised, the data cannot be reopened or

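### The sample-size paragraph cannot be reproduced from its own inputs: 2.573 is not the critical value for 0.017, and 47 per arm matches the printed formula only if the 10% loss allowance, described as still to be added, is already in it

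*Protocol*

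**What the plan says.** The Sample size section of the Protocol gives an unpooled normal-approximation formula for two proportions and all the values to put into it.

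- **Alpha:** 95% confidence, "adjusted using Bonferroni's correction for multiple comparisons to accommodate our three-arm design", printed as "0.05/3=0.017, critical value for 0.017=2.573".
- **Power:** 80%.
- **Water-only arm:** "Assuming 90% of children with facial Ct before washing still have facial Ct after washing in the water only arm".
- **Soap arm:** "60% of children with facial Ct before washing still have facial Ct after washing with water and soap".
- **Result:** 47 children with facial Ct per arm, said to come from that formula.
- **Loss:** "This target will be inflated by 10% to account for people being lost to follow-up".

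The same section then multiplies 47 by three to get 141, continues with "we need (141/0.6 =) 235 children with ocular Ct", and ends at 470 enrolled and 9,400 screened. The Intervention allocation section also uses groups of 47. The Statistical Analysis section says "Primary comparisons will be between Protocols A and B".

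**The concern.** Two things in the paragraph do not fit. The critical value printed beside the adjusted alpha is not the critical value for that alpha. And 47 is offered both as the direct result of the formula and as a target to which 10% will later be added, yet nothing is added further down the chain.

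A reader therefore cannot tell what significance level the trial was sized for, what n the formula gave, or whether 470 includes an allowance for loss. This matters in practice because the Study timescale section lets recruitment run until the sample size is reached in all three arms, so the field team needs one unambiguous target. If 47 really is the figure before inflation, the enrolment and screening targets leave out an allowance that the text promises.

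**Working it through.** **Inputs**, all from the Sample size section: p1 = 0.90, p2 = 0.60, power 80% (z = 0.8416), printed critical value 2.573, intended alpha 0.05/3. The formula is n = (z_alpha/2 + z_beta)² x [p1(1 − p1) + p2(1 − p2)] / (p1 − p2)².

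**1. Variance factor.** (0.09 + 0.24) / 0.30² = 0.33 / 0.09 = 3.667.

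**2. The plan's own figure.**
- With 2.573: (2.573 + 0.8416)² x 3.667 = 11.66 x 3.667 = 42.75, so 43 per arm. The stated figure is 47.
- With a 10% allowance: 42.75 x 1.1 = 47.03; dividing by 0.9 instead gives 47.50.

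So 47 is recovered from the printed formula only when the 10% is already inside it.

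**3. The critical value.**

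| Alpha | Two-sided z | One-sided z |
|---|---|---|
| 0.05/3 | 2.394 | 2.128 |
| 0.017 | 2.387 | 2.120 |

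Neither sidedness nor rounding gives 2.573. Working back, 2 x (1 − Φ(2.573)) = 0.0101.

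**4. The formula with the right value.** (2.394 + 0.8416)² x 3.667 = 38.39, so 39 per arm. With 10% loss: 39 x 1.1 = 42.9, so 43, or 39 / 0.9 = 43.3, so 44.

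**5. The recruitment chain** (x 3, / 0.6, / 0.5, / 0.05).

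| Basis | Per arm | Facial Ct | Ocular Ct | Enrolled | Screened |
|---|---|---|---|---|---|
| As printed | 47 | 141 | 235 | 470 | 9,400 |
| 47 inflated as the text says (x 1.1) | 52 | 156 | 260 | 520 | 10,400 |
| 47 inflated by / 0.9 | 53 | 159 | 265 | 530 | 10,600 |
| Right z, loss included | 43–44 | 129–132 | 215–220 | 430–440 | 8,600–8,800 |

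The printed row is 47 carried straight through, with no 10% entering at any step.

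**6. Power from the same formula**, Φ(0.30 / √(0.33/n) − z), with 47 per arm and with 42 (47 x 0.9 = 42.3).

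| n per arm | z = 2.573 | z = 2.394 |
|---|---|---|
| 47 | 84.3% | 88.2% |
| 42 | 79.1% | 83.9% |

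**The case against.** The strongest reply is that this is one slip of labelling plus one conservative slip in a z value, and that neither harms the trial. Most of that stands. The gap between 43 and 47 and the apparently missing inflation are the same 10% seen twice, so a reader should not count them as two independent errors. The larger z raises n rather than lowering it.

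It is also fair to say that nothing in the Protocol states that 47 is already inflated; its wording says the opposite. The match at 47.03 depends on rounding to the nearest child, since strict rounding up would give 48. Other methods also reach 47, for example a pooled one-sided calculation at 0.05/3 with 90% power. None of these is the printed formula with the printed inputs, so the inflated reading is likely but not proven, and the sponsor has to confirm it.

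The loss allowance also has limited bearing on the primary outcome. Under Procedure, the face is swabbed again about five minutes after washing. The withdrawal section keeps data collected up to withdrawal and replaces children withdrawn up to six hours after washing. The 42-per-arm case is therefore close to a worst case for the primary comparison.

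A reader might go further and infer that dividing alpha by three has no counterpart in the analysis, because only soap versus water is primary. The documents do not support that. Study Aim and Objectives also plans SuperTowel versus water and SuperTowel versus soap and water, which makes three pairwise contrasts. The alpha for each test may be set in the statistical analysis plan, which is not at hand.

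**Conclusion.** The point holds as an error of reporting and reproducibility that should be corrected. The printed critical value is wrong for the printed alpha (2.573 against 2.394), and the formula with the printed inputs gives 43 per arm, not 47. The text does not say consistently whether 47 is before or after the 10% allowance. On the literal reading, the chain is short of its own promise by about 50 enrolled children (520 against 470) and 1,000 screened (10,400 against 9,400).

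Three stronger conclusions might be drawn, and none is supported:

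- **That the trial is underpowered.** At the intended 0.05/3, 47 per arm gives about 88% power and 42 gives about 84%, both above the stated 80%.
- **That 80% power is reached only at alpha 0.010.** By the same formula it is also reached at 0.05/3 with 39 per arm.
- **That the primary test will be judged at 0.010.** That level is implied only by the z used for sizing; the level the text states is 0.017.

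These figures rest on the Protocol's own assumptions (90% versus 60% still positive, 60% of infected children with facial Ct, 50% of severe cases infected, 5% of screened children with severe inflammation) and on its unpooled formula. None of those assumptions is questioned here.

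**What to change.** In the Sample size section:

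1. Replace 2.573 with 2.394, the two-sided value for 0.05/3, and give the resulting n: 39 per arm before loss, 43 to 44 after a 10% allowance.
2. State the n before inflation separately from the n after it, and have the sponsor confirm which of the two 47 is.
3. **If 47 is after inflation:** reword the inflation sentence to say so, keep 470, and restate the power at alpha 0.0167 as about 88% with 47 analysable per arm and about 84% with 42.
4. **If 47 is before inflation:** the chain omits the promised 10%. Because the corrected formula needs only 39 per arm, remove the inflation claim and report the power of 47 per arm after 10% loss, about 84%.

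The cost is rewriting one paragraph. In either case 470 enrolled and 9,400 screened can stand, with no added participants.

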King et al. [20] argue that a 'dirty face' is not a good predictor of whether a face has been washed. They conducted a randomised trial of 424 children to receive a standardised face wash or none, and observed faces for ocular and nasal discharge, dust, food and flies at three time points through the day and at baseline. A significant difference was observed in the presence of ocular discharge (P < 0.001) and dry nasal discharge (P < 0.001) between the washed and unwashed groups, but two hours after washing, the presence of ocular discharge predicted face washing in only 63% of children, reducing to only 54% in four hours from washing.

In our own studies conducted in Phase 1 of Stronger SAFE (Ethics reference: 14325), we asked 34 children aged 1-9 with TF/TI to wash their faces with either water only or water and soap. Each child was given instructions about washing their face properly and was observed to follow these instructions. We found that washing with soap and water was more effective at removing ocular discharge than washing with water only (89% vs 27%, p = 0.003). In comparison, nasal discharge was not effectively removed by any method: discharge was removed from 27% of 11 children with nasal discharge at baseline by washing with soap, and 50% of 14 children by washing with water (p=0.250 for comparison with washing with soap). However, only two of these children enrolled (both randomly assigned to wash with water only) were positive for Ct by ocular swab, so we were unable to fully test our hypotheses that face washing would reduce Ct load on the face — the relevant agent for transmission of infection.

Facial hygiene measures and metrics

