Children aged 1-7 years with severe conjunctival inflammation (F3, P3) will be eligible to participate in the study. Children will be recruited following receipt of parental written informed consent.

Inclusion criteria

- Parental consent to take part
- Participant assent to take part
- Severe conjunctival inflammation (F3 and/or P3)
- Aged 1-7 years residents of Oromia State, Ethiopia
- Availability for study period (8 hours)

Exclusion criteria

- Known allergy to study materials
- Significant facial and/or ocular injury or pathology

Study timescale and withdrawal from the study

Trial screening and recruitment will continue until the sample size has been recruited in all three arms. All participants will be asked to participate for the full 8-hour observation period. Participants who experience adverse reactions to the face washing protocols (for example, an allergic reaction to the soap used) and/or wipe/swab specimen collection procedures will be withdrawn from the trial. Participants experiencing illness or adverse events not related to the trial will also be withdrawn. Data collected up to the point of withdrawal will still be used unless the participants explicitly requests that it is not.

Where a participant is withdrawn >6 hours after face washing, they will not be replaced. Where a participant is withdrawn ≤6 hours after face washing they will replaced by recruitment of an additional participant from the ongoing screening process. Participants will be able to withdraw by speaking to any member of the study team during the visit, or by contacting the study team using the contact information on the information sheet.

Intervention allocation

Recruited children will be randomised into one of three equally sized groups of 47 in the field. We will use a randomisation method appropriate to the field setting. For example, we might ask them to select a wrapped sweet (without looking) from a bag containing an equal number of different colours of sweet wrapper each indicating a different protocol.

The face washing interventions will be allocated to the three groups as follows:

- Group 1 (Protocol A) Face washing with water (control group)
- Group 2 (Protocol B) Face washing with water and soap (primary comparison)
- Group 3 (Protocol C) Face wiping with SuperTowel® (secondary comparison)

Protocol C - SuperTowel®

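### The count that ends recruitment is undefined: the protocol gives 470 enrolled, groups of 47 randomised, and 47 children with facial Ct per arm, and these are not the same target

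*Protocol*

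**What the plan says.** **Sizing.** The Sample size section works with children who have Ct on the face before washing. It takes residual facial Ct as 90% with water only ("Assuming 90% of children with facial Ct before washing still have facial Ct after washing in the water only arm") and 60% with soap ("60% of children with facial Ct before washing still have facial Ct after washing with water and soap"). It sets 80% power and a Bonferroni-adjusted critical value ("0.05/3=0.017, critical value for 0.017=2.573"), and arrives at 47 children with facial Ct per arm.

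**Conversion to enrolment.** The same section says "we expect 50% of children with severe inflammation (F3 and/or P3) to have ocular infection and 60% of those children with ocular Ct infection" are expected to have Ct on the face. From this it derives 470 children with F3 and/or P3, stated there as a minimum. The opening summary and the section on eligibility and recruitment give the same number as a total: "A total of 470 participants will be selected purposively following a screening process".

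**Randomisation.** The Intervention allocation section puts recruited children into three equal groups of 47.

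**End of recruitment.** "Trial screening and recruitment will continue until the sample size has been recruited in all three arms". Replacement is provided only for children withdrawn at or before 6 hours, not for children whose baseline face swab proves negative.

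**Analysis.** The Statistical Analysis section makes the analyses "restricted to children with *Ct* on their face at baseline as determined by PCR".

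**Checks on yield.** The eligibility section allows an optional rapid test in a subsample as quality assurance. The ancillary objectives, the Informed consent section and the Treatment of trachoma section describe the rapid test as part of screening. The last of these refers to test-negative children who were left out of the trial.

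**The concern.** The power statement concerns a count that is unknown when a child is enrolled. The only bridge from enrolled to analysed children is an assumed joint yield of 30%, and the stopping sentence does not say on which side of that bridge recruitment is counted. A field team could stop at 470 enrolled, at 47 randomised per arm, or at 47 confirmed per arm, and be following the text each time. Under the first reading, power depends on the yield. Under the second, the primary comparison would be badly underpowered. Only the third protects the stated power. A statistical analysis plan would not normally settle this, because the protocol itself sets the end of recruitment.

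**Working it through.** **Inputs, all from the protocol.** p1 = 0.90 and p2 = 0.60 (residual facial Ct, water only and soap); z for alpha = 2.573; z for 80% power = 0.8416; ocular yield 0.50; facial yield 0.60; three equal arms. The two-sided z for 0.05/3 is 2.394, not 2.573, so results are given with both.

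**Reproducing the plan's figures.**
- Variance term: 0.9 × 0.1 + 0.6 × 0.4 = 0.33. Squared difference: 0.30² = 0.09.
- n per arm = (2.573 + 0.8416)² × 0.33 / 0.09 = 42.75, so 43.
- 42.75 × 1.1 = 47.03. The stated 47 is therefore reproduced only if the 10% allowance for loss is already inside it, although the text describes the inflation as still to come.
- With z = 2.394: 38.4, so 39 per arm.
- Enrolment: 3 × 47 = 141; 141 / 0.6 = 235; 235 / 0.5 = 470; 470 / 0.05 = 9,400 screened. All are exact.

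**The three candidate targets, at the assumed yield.** Power = Φ(0.30 / √(0.33/n) − z), with n the analysable number per arm.

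| Reading of the sample size | Randomised per arm | Analysable per arm | Power, z = 2.573 | Power, z = 2.394 |
|---|---|---|---|---|
| 470 enrolled | 470/3 ≈ 157 | 470 × 0.3 / 3 = 47 | 84% | 88% |
| Groups of 47 randomised | 47 | 47 × 0.3 = 14.1 | 27% | 33% |
| 47 confirmed per arm | as many as needed | 47 | 84% | 88% |

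**Sensitivity if 470 is the stopping count** (facial yield held at 60%; the alternative ocular yields are illustrative).

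| Ocular yield | Analysable per arm | Power, z = 2.573 | Power, z = 2.394 |
|---|---|---|---|
| 50% | 47.0 | 84% | 88% |
| 45% | 42.3 | 79% | 84% |
| 40% | 37.6 | 74% | 79% |
| 30% | 28.2 | 58% | 65% |

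The joint yield needed for 80% power at 470 enrolled is 3 × 43 / 470 = 27% with the stated z, or 3 × 39 / 470 = 25% with 2.394. The plan assumes 30%.

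**Enrolment if 47 confirmed per arm is the stopping count:** 141 / (ocular yield × 0.6). This is 470 at 50%, about 588 at 40% (11,750 screened), about 784 at 30% (about 15,700 screened) and 1,175 at 20% (23,500 screened).

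**The case against.** **The text can be read correctly.** The Sample size section gives 470 as a minimum and as the means of finding 141 children with facial Ct, and the stopping sentence is open-ended. It may already mean 47 confirmed per arm. This stands: a reader might infer that recruitment is fixed at 470, and the document does not establish that. It establishes only that the target is not stated.

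**The design is adequate if its assumptions hold.** This also stands. Because 80% power needs 43 rather than 47 per arm, there is some room for chance variation. With 157 randomised per arm and a 30% yield, the probability that the realised arm sizes still give at least 80% power is about 82% with z = 2.573 and about 97% with z = 2.394. Failing to reach exactly 47 is not in itself a loss of the stated power.

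**The earlier washing study.** A reader might set the assumed 50% against the group's earlier study of 34 children, in which "only two of these children enrolled (both randomly assigned to wash with water only) were positive for Ct by ocular swab". The documents do not support using it that way. Those children were aged 1–9 with TF/TI and were not selected for F3/P3. The 50% is attributed to other project data. The new trial also targets high-prevalence communities and recruits contacts of infected cases. The result shows that too few infected children can defeat such a study, which is a reason to track the yield. It does not estimate the yield here.

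**Yield is not wholly unchecked.** The rapid test bears on the ocular step, and if it gates entry, the 50% step largely disappears. The pilot swabs the faces of up to 20 ocular-positive children. But the rapid test carries no threshold or action, its role differs between sections, and neither check is linked to the enrolment number.

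**Conclusion.** The concern holds as an undefined and internally inconsistent recruitment target, not as a trial fixed at 470 or a yield shown to be wrong. If 470 are enrolled and both yields are as assumed, power is about 84% on the plan's own terms. A fall in ocular yield from 50% to 40% takes it to about 74% (79% with z = 2.394). Taking the allocation section literally leaves about 14 analysable children per arm and about 27% power (33%). These figures rest on residual proportions of 90% and 60%, a 60% facial yield, equal arms and the plan's normal-approximation formula, which is rough at 14 per arm. The mismatch between 2.573 and 0.05/3 is a separate point; it makes the plan's number larger, not smaller. This should be corrected before recruitment.

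**What to change.** In the section on study timescale and withdrawal, state that recruitment ends when each arm holds 47 children with a PCR-positive baseline face swab and a valid immediate post-wash swab. Count positivity from baseline swabs only. Judge the post-wash swab valid from the laboratory's sample log, so that no post-wash Ct result is seen.

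Keep 470 enrolled and 9,400 screened as planning figures and add a stated enrolment ceiling. If the ceiling is reached first, report the power at the number analysed. A ceiling is needed because an uncapped rule could become very costly at a low yield, as the enrolment figures above show.

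In the Intervention allocation section, replace the groups of 47 with the number actually randomised per arm, about 157 if 470 are enrolled. State whether 47 already includes the 10% allowance. Reconcile whether the rapid test decides entry or is an optional quality check, and restate the 50% step accordingly. If the earlier 2 of 34 is mentioned, use it only as the reason for tracking yield.

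The cost is protocol wording plus testing baseline face swabs during recruitment; samples already go to the laboratory weekly. The downsides are that total enrolment is not fixed in advance and that some over-recruitment is likely while results are awaited.

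### The allocation section sets randomised groups of 47, but 47 is the number per arm needed with facial Ct at baseline; the enrolment plan implies about 157 randomised per arm

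*Protocol*

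**What the plan says.** - Sample size: "47 children with Ct on their faces will be needed in each trial arm". The 47 is a count of children already positive on the face, and the text says the target will be inflated by 10% for loss to follow-up.
- Sample size, continued: half of children with F3 and/or P3 are expected to have ocular Ct, and 60% of those to have facial Ct. The chain runs from 141 to 235 to at least 470 enrolled.
- Participant eligibility and recruitment: "A total of 470 participants will be selected purposively following a screening process". The opening summary gives the same total and has the recruited children randomised into three equal groups.
- Intervention allocation: "Recruited children will be randomised into one of three equally sized groups of 47 in the field".
- Study timescale and withdrawal from the study: "Trial screening and recruitment will continue until the sample size has been recruited in all three arms". No number is attached.
- Statistical Analysis: the analyses are "restricted to children with *Ct* on their face at baseline as determined by PCR".

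**The concern.** One figure carries two meanings. In the Sample size section 47 per arm is the number of children who can enter the primary analysis. In the allocation section it is the number of recruited children put into each arm. The implied randomised totals, 141 and 470, differ by a factor of 3.3.

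The allocation figure cannot refer to known positives. The only disease criterion for entry is F3 and/or P3. The baseline face swab is taken at the same visit as the wash (Procedure, steps 9 and 10), and samples go weekly to the Adama laboratory for PCR (Laboratory Procedures). Nobody in the field knows a child's facial Ct status at allocation.

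The allocation section is what anyone preparing the allocation materials, or monitoring adherence, would work from. The stop rule comes just before it and does not settle the matter. If 47 were taken as the target, the primary comparison of soap and water with water only would be far too small.

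**Working it through.** **Inputs (Protocol, Sample size).** p1 = 0.90: "Assuming 90% of children with facial Ct before washing still have facial Ct after washing in the water only arm". p2 = 0.60: "60% of children with facial Ct before washing still have facial Ct after washing with water and soap". Power is 80%. Alpha and critical value: "0.05/3=0.017, critical value for 0.017=2.573". The two-sided critical value for 0.05/3 is 2.394; 2.573 corresponds to a two-sided alpha of about 0.0101. Both are used below.

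**Step 1: reproduce 47.** The formula is n = (Z_alpha/2 + Z_beta)^2 x [p1(1-p1) + p2(1-p2)] / (p1-p2)^2.
- With 2.573: (2.573 + 0.842)^2 x 0.33 / 0.09 = 42.75, i.e. 43 per arm.
- 42.75 x 1.10 = 47.0.
- With 2.394 the formula gives 39.

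So 47 reproduces from the printed formula and critical value only if the 10% is already inside it.

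**Step 2: reproduce the enrolment.** 3 x 47 = 141; 141/0.6 = 235; 235/0.5 = 470. Split equally, 470/3 = 156.7 per arm, and 156.7 x 0.5 x 0.6 = 47. The chain is consistent if all 470 are randomised.

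**Step 3: take the allocation section literally.** 47 x 0.5 x 0.6 = 14.1, so about 14 per arm are analysable (42 of 141).

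**Step 4: power at 14 per arm, 90% versus 60%.** SE = sqrt(0.33/14) = 0.1535; 0.30/0.1535 = 1.954.
- Alpha 0.05/3: Phi(1.954 - 2.394) = 33%.
- Printed 2.573: Phi(1.954 - 2.573) = 27%.
- Unadjusted 0.05: Phi(1.954 - 1.960) = 50%.

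Sensitivity to the test, at 14 per arm:

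| Test | 2.573 (alpha about 0.0101) | alpha 0.05/3 | alpha 0.05 |
|---|---|---|---|
| Protocol's formula (unpooled) | 27% | 33% | 50% |
| Pooled normal test | 22% | 27% | 45% |
| Fisher's exact | 10% | 18% | 32% |

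**Step 5: if only ocular-positive children entered.** 47 x 0.6 = 28 per arm. SE = sqrt(0.33/28) = 0.1086; 0.30/0.1086 = 2.763. Power is Phi(2.763 - 2.394) = 64%, or Phi(2.763 - 2.573) = 58% with the printed value.

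**Step 6: the intended plan.** With 47 analysable per arm, SE = 0.0838 and 0.30/SE = 3.580. Power is 88% at alpha 0.05/3, or 84% with 2.573. With 10% lost (about 42 per arm) it is 84% or 79%.

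**Step 7: if the 10% is still to be added to 47.** Enrolment becomes 470 x 1.10 = 517, or 470/0.9 = 522.2, rounded up to 523.

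**The case against.** The strongest reply is that the document largely answers the question itself. The total of 470 appears in the opening summary, in the Sample size section as a minimum, and again under recruitment with a matching plan to screen about 9,400 children. Against that stands one sentence. This reply stands: 470 is the intended total, and the sentence is most likely a slip and not a second design.

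A reader might infer that recruitment will close at 141 children and that the trial has about one third power. The documents do not support this. The stop rule gives no number, and its mention of the sample size can equally be read as pointing to the Sample size section. The low power is conditional on following the allocation sentence to the letter. The 33% also uses the correct critical value for 0.05/3; the printed one gives 27%.

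It can also be said that 14 per arm assumes no test for infection before entry. The Treatment of trachoma section mentions children with a negative rapid test who were not included. The recruitment section, however, describes that test as something a subsample may have for quality assurance, and the inclusion criteria do not require it. Even if it did filter entry, Step 5 leaves power below 80%.

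The trial overview figure is not in the text available, so any per-arm numbers in it could not be compared.

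**Conclusion.** The allocation section is wrong as written. Its group size contradicts the Sample size section, the recruitment target and the equal three-way split in the opening summary. The intended randomised size is about 157 per arm, and 47 is the expected number of those with facial Ct at baseline.

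Followed literally, the sentence would leave about 14 analysable per arm. Power by the Protocol's formula would be about 33% at alpha 0.05/3 (27% with 2.573). Across tests at alpha 0.05/3 or 0.05 the range is about 18% to 50%; the exact test at the alpha implied by 2.573 is lower still. These figures rest on the Protocol's own assumptions of 50% ocular infection, 60% facial Ct among those infected, and 90% versus 60% after washing. If 470 are randomised as the other sections plan, power is not lost and only the wording is at fault.

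Whether 470 already allows for loss is unsettled. The arithmetic suggests that it does, while the text says the allowance is still to be applied.

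**What to change.** 1. In Intervention allocation, replace the groups of 47 with about 157 randomised per arm (at least 470 in total), expected to yield about 47 per arm with facial Ct at baseline.
2. In Study timescale and withdrawal from the study, define the sample size in the same terms. Keep the total as a minimum: a hard stop at 470 would lock in a shortfall if fewer than 30% of enrolled children have facial Ct.
3. In Sample size, state whether 47 already includes the 10% for loss. If it does, say so and leave 470. If it does not, restate the enrolment as about 517 to 523, depending on whether one multiplies by 1.10 or divides by 0.9.

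Items 1 and 2 cost only wording and leave the planned enrolment as it is. Item 3 is also wording if the allowance is already inside 47; otherwise it adds about 47 to 53 children.
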